8.1.7 Conversion factors

The following conversion factors will be used to convert days into months or years: 1 month = 30.4375 days, 1 year = 365.25 days.

8.1.8 Reporting Conventions

Quantitative variables will be summarized using descriptive statistics (by visit, when appropriate) and will consist of values for number of evaluable subjects, mean, standard deviation (SD), median,Q1, Q3, minimum, and maximum. In calculated statistics, mean, median, Q1, and Q3 will be displayed with one more digit than original data while the SD will be displayed with two more digits. Minimum and maximum will keep the same number of decimal digits as the original data.

Statistics	Format
Ν	ХХ
n	ХХ
Mean	X.X
SD	X.XX
Median	X.X
Q1, Q3	x.x, x.x
Min, Max	х, х
SE	x.xx
95% CI	[x.x, x.x]
P-Value	0.XXX
Missing	ХХ
Percentage	x.x%

Table 2 Presentation of Numbers

N = total number of subjects in the defined analysis set; n = total number of subjects in the specific category. If N is specified in the column heading, then any reference to the number of subjects in the body should be no larger than N.

Qualitative variables are summarized by counts and percentages and displayed by decreasing order of modalities if ordinal, and by alphabetical order otherwise. The number of subjects with missing data should be displayed when there is missing data (number of total evaluable subjects is less than number of total subjects in the defined analysis population set). The numerator is the total number of evaluable subjects in the specific category (n).

Unless otherwise stated, for percentages:

- One decimal digit should be given
- No percentage should be given for cells with 0 subjects
- Based on the number of subjects in the analysis set
- Counts of missing observations will not be included in the denominator, but will be presented.

8.1.9 Presentation of Tables/Listings/Figures:

The treatment label for all Tables, Listings, and Figures will be: NeuWave MW Ablation.

All data recorded during the trial will be presented in individual data listings on the SAF, unless otherwise specified (including scheduled and unscheduled data). All listings will be sorted by phase (main or run-in), site, subject, parameter, date, and time point (where applicable), if not otherwise stated. Further details are provided in the appropriate section for the analysis of the specific parameter.

Tables and figures will be presented by scheduled time point (where applicable), unless otherwise specified. By-visit tables and figures will be sorted by chronological scheduled time point (where applicable).

8.1.10 Software

All analyses will be conducted using SAS version 9.4 or higher.

8.2 Disposition of Study Subjects

Subject disposition will be summarized for the SCR. The number and percentage of subjects screened, screen failure, treated, completed and discontinued will be tabulated along with the specific reasons for discontinuation. Analysis population (ENR, Run-in, FAS, PPS and SAF) will be presented. Listing of subject disposition and eligibility criteria will be prepared.

Counts and percentages of protocol deviations (PD) recorded during the study will be provided for the type of deviation, the rationale for the deviation, and classification (minor or major). Listing of protocol deviations will be presented for SAF population. Sort by phase (main or run-in), site, subject ID, and date of deviation.

8.3 Demographic and Baseline Characteristics

8.3.1 Demographics

Demographic data and other baseline characteristics will be presented for the FAS and Run-in analysis set.

The following demographic and other baseline characteristics will be reported for this study:

- Sites
- Age (years) at informed consent date
- Age category: <= 65 years, and > 65 years
- Sex (including childbearing potential of female subjects)
- Ethnicity
- Race
- Pregnancy Test Result
- Alcohol Use
- # of target tumor(s) (1,2,3)
- Baseline ECOG performance status (0-2)
- Baseline Child-Pugh score
- Baseline ASA score
- Baseline NPRS Pain score

8.3.2 Baseline Target Tumor Assessement (Analyzed on tumor level)

Baseline target tumor assessment will be summarized for FAS and Run-in

In "[Target Tumor Assessments]" CRF page, maximum tumor dimension, tumor type and vertical dimension be summarized, same as other continuous measurement for each target lesion. Counts for liver segment and major vessel assessment will be tabulated at baseline.

Other details on Target tumor assessments will only be listed, sorted by phase, site, subject, target tumor.

8.3.3 Medical History and Surgical History

General medical history will be presented for the FAS and Run-in. Number and percentage of subjects with at least one medical history will be tabulated by System Organ Class (SOC) and Preferred Term (PT). Medical history will be coded using the MedDRA codes (MedDRA version 22.0 or above). A listing of all subject medical histories will be prepared.

Surgical histories and radiotherapy hstories will also be presented in a listing for the SAF.

8.3.4 Prior and Concomitant Medications and Procedures

Medications and procedures will be presented for the SAF. Medications will be presented by preferred term. Medications will be coded using the World Health Organization Drug Dictionary (WHO-DD) latest version.

Prior medications are defined as the medications/therapies that were taken and ended prior to the procedure; while concomitant medications are defined as the medications/therapies with end date after the procedure (Day 0 but after the procedure, or after Day 0) or ongoing medication/therapies.

Summary of indications for concomitant medications and procedures(indication, related to AE or not) will also be tabulated.

Prior and concomitant medications and procedures will be listed.

8.4 Effectiveness and Safety Endpoint(s) and Associated Hypotheses

In this study, all analyses are for descriptive purpose only. No hypothese testing will be conducted on the effectiveness and safety endpoints.

8.4.1 Effectiveness Endpoint(s)

All effectiveness endpoints will be summarized for FAS and PPS. Subjects in run-in analysis set will be also summarized for technical success and technical efficacy endpoints.

The effectiveness endpoints are defined, as follows:

Technical Success

Technical Success, defined as a combination of A0 ablations (complete tumor ablation with a surrounding 5 mm margin) and A1 ablations (complete tumor ablation with inadequate margins) based on contrast-enhanced MRI performed at Visit 2B (up to 7 days following the original ablation procedure).

The number and percentage of tumors achieving Technical Success will be summarized. Percentage will be calculated relative to the total count of evaluable target tumor lesions at Visit 2B. A 95% confidence interval will be estimated using wald method. The number and percentage of tumors with A0, A1 and A2 margins will be presented as a sub-categorization :

Note: Ablation evaluation by Investigator is collected in "Ablation Zone Assessment" CRF page. A0: complete tumor ablation with adequate margin (surrounding 5 mm margin) A1: complete tumor ablation with inadequate margins

A2: Incomplete tumor ablation

A subject archieving technical success is defined as a subject with all tumors reaching A0 or A1 at Visit 2B. The number and percentage of subjects archieving Technical Success will be summaried as well. Percentage will be calculated relative to the total number of subjects in relavent analysis population (FAS or PPS). A 95% confidence interval will be estimated using wald method.

Number and percentages of reasons for A1 and A2 ablation categorization will be also summarized.

Technical Efficacy

Technical Efficacy, defined as a combination of A0 ablations (complete tumor ablation with a surrounding 5 mm margin) and A1 ablations (complete tumor ablation with inadequate margins), based on contrast-enhanced MRI scans at Visit 3 (1 month +/- 7 days) after the original ablation procedure.

Tumor-level analysis method is same as that of primary endpoint. The number and percentage of tumors achieving Technical Efficacy will be summarized and a 95% confidence interval will be estimated using Wald method. The number and percentage of tumors with A0 and A1 margins will be presented as a sub-categorization within each presentation of Technical Efficacy, as well as a summarization for the number and reasons for repeat ablations through Visit 3.

A subject archieving technical efficacy is defined as a patient with all tumors reaching A0 or A1 at Visit 3. The number and percentage of subjects archieving Technical Efficacy will be summaried as well. Percentage will be calculated relative to the total number of subjects in relavent analysis population (FAS or PPS). A 95% confidence interval will be estimated using wald method. But the subjects who have any A2 margin since the visit 2B scan would not be counted as technical efficacy regardless if the tumor was corrected with repeat ablation.

Local tumor progression (LTP) (the 2nd interim, final)

LTP is evaluated after the ablation of the target tumor(s). LTP describes the appearance of tumor foci at the edge of the ablation zone, after at least one contrast-enhanced follow-up

MRI scan has documented adequate ablation, and an absence of viable tissue in the target tumor and surrounding ablation margin, by using imaging criteria.

Tumor-level analysis method is same as that of Technical Success endpoint. The number and percentage of tumors with LTP will be summarized and a 95% confidence interval will be estimated using Wald method.

A subject with LTP is defined as a patient with any target tumor LTP. The number and percentage of subjects with LTP. Percentage will be calculated relative to the total number of subjects in relevant analysis population (FAS or PPS).

Subgroup analysis is defined in SAP section 8.11. Two subgroup columns (subjects/tumors with only initial ablation and subjects/tumors with repeat ablation) and 1 total column will be used as analysis columns in LTP tables.

Tumor type (primary HCC and recurrent HCC and other) will be another subgroup variable for LTP (analyzed for patient level and tumor level).

LTP start date is the date of initial ablation of a subject. The event date of LTP is collected in "Ablation Zone Assessment" CRF page as following table:

		Event/Censoring	
	Situation	Date	Outcome
No post-base	eline or no baseline Ablation Zone A	ssessment	
	No post-baseline local tumor	Date of initial	
A1	evaluation	ablation	Censored
	No baseline local tumor	Date of initial	
A2	evaluation	ablation	Censored
With baselin	e and post-baseline tumor assessm	ents	
	Local Tumor Progression and zero or one missed tumor assessment prior to confirmed		
B1	LTP	Date of first LTP date	Event
	Local Tumor Progression and over one missed tumor assessment prior to confirmed	Date of the latest evaluable local tumor assessment prior to the missed	
B2	LTP	assessment	Event
		Date of last local	
		tumor assessment	
	No progression, either alive or	with no documented	
С	death	LTP	Censored

Table 3: Censoring Rules for LTP

		Date of last tumor assessment with no documented	
D	Dead	progression	Censored
		Date of last tumor	
		assessment with no	
		documented	
E	Withdrawal by Subject	progression	Censored

Local tumor progression rates at 3, 6, 9, 12, 18, 24, 30, and 36 months will be estimated using the Kaplan-Meier (K-M) method and 95% confidence intervals (Greenwood's formula) will be provided.

The K-M curve of time to LTP will be provided.

Secondary efficacy rate (the 2nd interim, final)

Secondary efficacy rate is defined as the percentage of subjects whose tumors have undergone successful repeat ablation following identification of local tumor progression at any time during study follow up.

It could be found in CRF page, Ablation Zone Assessment, "Re-ablate with Neuwave". For subgroup that has LTP and used Certus to re-ablate, the number and percentage of subjects achieving secondary efficacy, will be summarized and a 95% confidence interval will be estimated using wald method.

Progression-free survival (PFS) (the 2nd interim, final)

PFS is defined as length of time from initial ablation until disease progression.

Table	e 4. Censoring Rules for PFS		
	Situation	Event Date	Outcome
No po	st-baseline or no baseline Ablation Zo	ne Assessment	
	No post-baseline tumor evaluation		
A1	and alive	Date Ablation performed	Censored
	No post-baseline tumor evaluation		
	but died on or before the second		
A2	scheduled tumor assessment	Date Ablation performed	Censored
With baseline and post-baseline tumor assessments			

Table 4: Censoring Rules for PFS

В	Any Tumor Progression and zero or one missed tumor assessment prior to progression	Date of first progression	Event
		Date of last progression	
	PD happens after >=2 consecutively	assessment before	
С	missing tumor assessment	missing assessments	Censored
		Date of last progression	
		assessment with no	
D	No progression	documented progression	Censored

Progression-Free Survival rate will be estimated using the Kaplan-Meier method and 95% confidence intervals (Greenwood's formula) will be provided for 6, 12, 18, 24, 30, 36 months.

The K-M curve of time to progression will be provided.

Progression-free survival (PFS) sensitivity analysis (the 2nd interim, final)

PFS is defined as length of time from initial ablation until disease progression or death, whichever comes first.

Overall survival (OS)

36-month OS is measured from the time of the first ablation procedure to the time of death or last follow-up, if death has not occurred.

For OS, death from any cause will be considered as an event. If no death is reported, then use the cut-off date as the censored date of OS.

Overall Survival rate will be estimated using the Kaplan-Meier method and 95% confidence intervals (Greenwood's formula) will be provided.

The K-M curve of time to death will be provided.

Quality of Life (QoL)

EORTC QLQ-C30

The EORTC QLQ-C30 (version 3.0) comprises 30 questions and provides a multidimensional assessment of QoL. The QLQ-C30 is composed of both multi-item scales and single-item measures. EORTC QLQ-C30 can be combined to produce 5 functional scales (Physical, Role, Cognitive, Emotional, and Social), 3 symptom scales (Fatigue, Pain, and Nausea/vomiting), 5 individual items (dyspnea, insomnia, appetite loss, constipation, and diarrhea) and a global measure of health status. Each of the multi-item scales includes a different set of items - no item occurs in more than one scale. All of the scales and single-item measures range in score from 0 to 100. A high scale score represents a higher response level.

There are four items for each question (from Q1 to Q28): from not at all, a little, quite a bit, to very much, each will be considered as from 1 to 4. For Q29 and Q30, will be scored from 1 to 7.

No response (NR) will not be considered as missing and not included in the analysis.

Scale	Number of items	ltem range*	Item numbers
Global health status / QoL			
Global health status/QoL	2	6	29, 30
Functional scales			
Physical functioning	5	3	1 to 5
Role functioning	2	3	6, 7
Emotional functioning	4	3	21 to 24
Cognitive functioning	2	3	20, 25
Social functioning	2	3	26, 27
Symptom scales / items			
Fatigue	3	3	10, 12, 18
Nausea and vomiting	2	3	14, 15
Pain	2	3	9, 19
Dyspnoea	1	3	8
Insomnia	1	3	11
Appetite loss	1	3	13
Constipation	1	3	16
Diarrhoea	1	3	17
Financial difficulties	1	3	28

Table 5: Scoring the EORTC QLQ-C30 version 3.0

* *Item range* is the difference between the possible maximum and the minimum response to individual items; most items take values from 1 to 4, giving *range* = 3.

The scoring procedure is as follows:

Step1: For all scales, the raw score (RS) is calculated as mean of the component items:

RawScore =
$$RS = (I_1 + I_2 + ... + I_n)/n$$
.

If at least half of the component items from the scale have been answered, the raw score is calculated as the average of the non-missing items, otherwise set to missing.

Step 2: Scale score (S) is calculated by a linear transformation to 0-100:

For Functional scales:

Score = S =
$$\left(1 - \frac{RS-1}{Range}\right) \times 100$$

For Symptom scales / items and Global health status / QoL:

Score = S =
$$\left(\frac{RS-1}{Range}\right) \times 100$$

where Range is the difference between the maximum possible value of RS and the minimum possible value. The EORTC QLQ-C30 has been designed so that all items in any scale have the same range. Therefore, the range of RS equals the range of the item values. Most items are scored 1 to 4, giving range = 3. The exceptions are the items contributing to the global health status / QoL, which are 7-point questions with range = 6.

Higher scores for the global health status/ QoL scale and functioning scales indicate a higher/healthier level of functioning and a higher/better QoL respectively, whereas higher scores in symptom scales represent a higher level of symptoms/problems.

Example:

Emotional functioning (EF), Raw score (RS) = (Q21+Q22+Q23+Q24)/4EF score = $\{1 - ((RS - 1)/3)\}$ *100

If at least half of the items (i.e. 3 of 6 items, or 3 of 5 items) from the domain have been answered, assume that the missing items have values equal to the average of those items which are present for that respondent. This is equivalent to the raw score being taken as the mean of the non-missing item values. As a result none of the single-item measures can be imputed, i.e. if a single-item measure is missing, the subscale is missing.

Example:

Emotional Functioning if Q23 is missing (i.e. 3 items are not missing) Raw Score (RS) = (Q21+Q22+Q24)/3EF Score = $\{1 - ((RS - 1)/3)\}$ *100

All of the scales and single-item measures are linearly transformed so that each score ranges from 0 to 100.

The EORTC QLQ-C30 Summary Score is calculated from the mean of 13 of the 15 QLQ-C30 scales (the Global Quality of Life scale and the Financial Impact scale are not included).

Prior to calculating the mean, the symptom scales need to be reversed to obtain a uniform direction of all scales. The summary score will only be calculated if all the required 13 scale scores are available (using scale scores based on the completed items, provided that at least 50% of the items in that scale have been completed.)

Observed values by visit and changes from baseline in EORTC QLQ-C30 scores in each scale/domain and totally are presented as n, mean, SD, median, Q1, Q3, minimum, and maximum. In addition, raw scores of EORTC QLQ-C30 are listed.

The changes from baseline in EORTC QLQ-C30 scores in each scale/domain and totally are presented as mean, 95%CI and p value compare with 0.

Liver-specific EORTC QLQ-HCC18

EORTC QLQ-HCC18 includes 18 multi-item scales. These items are grouped into 6 domains namely fatigue, body image, jaundice, nutrition, pain, and fever. Two remaining single items address abdominal swelling and sex life. All scales are grouped and converted to score 0 to 100 according to the scoring manual; a higher score represents a more severe symptom or problem.

Scale	Number of items	ltem range*	Item numbers
Symptom scales / items			
Fatigue	3	3	15. 16, 17
Body Image	2	3	3, 5
Jaundice	2	3	6, 7
Nutrition	5	3	1, 2, 12, 13, 14
Pain	2	3	8, 9
Fever	2	3	10, 11
Abdominal Swelling	1	3	4
Sexual Interest	1	3	18

 Table 6 Scoring the EORTC QLQ-HCC18

* *Item range* is the difference between the possible maximum and the minimum response to individual items; most items take values from 1 to 4, giving *range* = 3.

The scoring procedures as below:

For each of these domains, a symptom score is computed by taking the following steps:

- (1) sum across the item responses on that domain,
- (2) divide by the number of non-missing items to obtain the mean of item response (RS),
- (3) subtract 1 from the mean of the item responses (i.e., item response mean -1),
- (4) divide by the number in Item Range
- (5) multiply by 100.

This results in symptom scores that range from 0 to 100 with higher scores indicating greater symptom severity. These symptom scores can be computed as long as at least 50% of the items have responses (i.e., 1 item response needed for 1 item domains, 1 item response needed for 2 item domains, 2 item responses needed for 3 item domains).

HCC18 index-score was defined as the sum of all 8 QLQ-HCC18 symptom/problem scales divided by 8 (the total number of QLQ-HCC18 scales). A higher HCC18 index-score reflects a worse overall HRQOL.

Observed values by visit and changes from baseline in EORTC QLQ-HCC18 scores in each domain and totally are presented as n, mean, SD, median, Q1, Q3, minimum, and maximum. In addition, raw scores of EORTC QLQ-HCC18 are listed.

The changes from baseline in EORTC QLQ-HCC18 scores in each scale/domain and totally will be estimated by mean, SE, 95%CI and p value.

Health Economics (the 1st interim)

Health economics will be summarized for the FAS and run-in. Procedure details, device information (as described in the "ABLATION" CRF page), and hospital discharge (as described in the "DISCHARGE FORM" CRF page) will be summarized by ablation (initial only vs repeat ablation) and listed.

- Complete Procedure Time
- Length of hospital stay.
- Ablation Time
- Number of Ablations
- Max Power
- Max Temperature
- Max Number of Probes of Each Type (PR, LK, and SR) and Overall
- Number of Probe RepositionNumber of ultrasound/CT scans performed for probe assessment
- Number of ultrasound/CT scans performed for margin assessment
- Other Ablation related information will be listed.

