The largest clinical experience using MW ablation to treat HCC comes from China, in part due to early adoption of MW ablation systems available only in Asia. That multicenter study of 1007 patients with primary liver cancer showed a technical success of 97.1% (1276/1363) and a local tumor progression rate of 5.9% (78/1363) with a mean follow-up time of 17.3 months (range, 3-68.9 months). The 1-, 3- and 5-year overall survival rates were 91.2%, 72.5% and 59.8%, respectively.⁵

A retrospective study of MW ablation as a first-line treatment for HCC evaluated the long-term outcomes and prognostic factors of 221 consecutive patients receiving MW ablation in Renji Hospital (Shanghai) between October 11, 2010 and December 31, 2013 were enrolled. Technique effectiveness was evaluated 1-month post-ablation. Initial complete ablation was found in 201 (90.95%) patients, secondary technique effectiveness in 8 (3.62%) patients, and the remaining 12 (5.43%) patients suffered from incomplete ablation after 2 sessions of MW ablation. No patients died within 30 days post ablation. Major complications occurred in 8 (3.8%) patients. It was concluded that MW ablation provides high technique effectiveness rate and is well tolerated in patients with HCC as a first-line treatment.

Confidential Page 21 of 61

Literature Review

Pre-clinical and clinical data has shown that MW ablation is safe and effective in liver tumors with low complication rates, high rates of technical success, lower rates of local tumor progression and promising disease-free and overall survival rates than have historically been reported for radiofrequency (RF).⁷

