4.2. Application of Investigational Product

Thermal ablation is increasingly utilized in the treatment of primary and metastatic liver tumors, both as curative therapy and as a bridge to transplantation. Recent advances in high-powered MW ablation systems have allowed physicians to realize the theoretical heating advantages of MW energy compared with other ablation modalities. As a result, there is a growing body of literature detailing the effects of MW energy on tissue heating, as well as its effect on clinical outcomes.¹³

Multiple-Antenna Microwave Ablation

Several reports have demonstrated that multiple-antenna MW ablation is safe and improves treatment efficacy. Multiple antennas were used in the studies by Simon et al¹⁴ and Meredith et al¹⁵ described above. In addition, Yu et al¹⁶ treated nine patients with intraoperative MW prior to resection of HCC. The ablations were performed with a single straight antenna, three straight antennas, or three looped antennas. The coagulation volumes were significantly larger for the three-antenna configurations and the study showed that multiple antennas are a promising way to safely, rapidly and effectively treat large HCCs. Uniform cell kill within the ablation zone was also seen in this study.

Microwave Ablation with a Gas-Cooled System

The results of HCC treatment with a high-power, gas-cooled, multiple antenna-capable MW device were retrospectively reviewed by Ziemlewicz et al. ¹⁷ A total of 107 HCCs in 75 patients were treated via percutaneous approach. All procedures were performed with a single MW system (Certus) with one to three 17-gauge antennas. Primary technique effectiveness rate was 91.6% (98 of 107) overall. Ziemlewicz concluded that treating HCC with a gas-cooled, multiantenna-capable MW ablation device is safe, with promising treatment effectiveness.

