The visit in the outputs should be derived based on the above visit schedule.

If a visit is performed "out of window" (i.e.between two visit windows), the visit should be analyzed as part of the the visit closest in terms of time or number of days as outlined by visit schedule, above. More details can be found in Table 1 of the protocol.

In case any retest performed within one visit, the visit in the outputs will be derived based on the above time windows. The visit with worst result will be used as the planned visit.

5 Levels of Significance

Given that no hypotheses are formally being tested in this study, no levels of significance are specified. Estimation of specified study endpoints will be performed using two-sided 95% confidence intervals (CI).

6 Analysis Sets

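### SAP 8.4.1 fixes Wald 95% intervals with no fallback for small denominators or rates near 0% or 100%; the secondary efficacy rate is the endpoint most exposed

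*SAP*

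**What the plan says.** SAP section 5 sets the standard: "Estimation of specified study endpoints will be performed using two-sided 95% confidence intervals (CI"). SAP 8.4.1 then chooses the method. For Technical Success, at tumour and subject level: "A 95% confidence interval will be estimated using wald method". Technical Efficacy is treated the same way at both levels. For LTP: "The number and percentage of tumors with LTP will be summarized and a 95% confidence interval will be estimated using Wald method". For secondary efficacy, restricted to subjects who have LTP and are re-ablated with Certus: "the number and percentage of subjects achieving secondary efficacy, will be summarized and a 95% confidence interval will be estimated using wald method".

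Neither document gives an exact or score interval, a truncation rule, a continuity correction or a minimum sample size. SAP 8.9 (subgroups) and 8.10 (sites) ask for 95% intervals without naming a method. SAP 8.4.1 also summarises the run-in set (12 subjects) for Technical Success and Technical Efficacy, without mentioning an interval. SAP 8.4 states that "all analyses are for descriptive purpose only".

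**The concern.** The Wald interval is p ± 1.96·√(p(1−p)/n). It has zero width when every subject succeeds or every subject fails, whatever n is. It passes 100% when failures are few, and it covers less than 95% when n is small or the rate is extreme. Ablation success rates lie where this happens, and secondary efficacy adds a small denominator. Tumour-level intervals have a further gap: a patient may contribute up to 3 tumours, and the formula has no within-patient term.

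The trial tests no hypothesis. Protocol 8.4 sets no acceptability criterion and judges the device against other available therapies. Estimates with intervals are therefore the only inferential output, and an interval labelled 95% should come close to that.

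**Working it through.** **Plan's own sample size.** 100/(1 − 0.20) = 125, plus 4 × 3 = 12 run-in subjects, gives 137. This reproduces SAP section 7.

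**Denominator for secondary efficacy (not stated in the documents).** Protocol 4.1.1 cites a "local tumor progression rate of 5.9% (78/1363) with a mean follow-up time of 17.3 months". The printed fraction is 5.7%; both values are carried.
- Direct bound: 78 events in 1007 patients is at most 7.7% of patients, and 125 × 78/1007 = 9.7.
- Second route, assuming 75/15/10% of patients have 1/2/3 independent tumours: 0.75q + 0.15(1−(1−q)²) + 0.10(1−(1−q)³). At q = 0.059 this is 7.8%, or 9.8 of 125; at 5.7% it is 9.5.
- Follow-up here is 36 months, which raises the number. LTP not re-ablated with Certus lowers it. A range of 5 to 20 is assumed.

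**Intervals at n = 10 (%).**

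| Result | Wald | Wilson | Clopper-Pearson |
|---|---|---|---|
| 10/10 | 100 to 100 | 72.2 to 100 | 69.2 to 100 |
| 9/10 | 71.4 to 108.6 | 59.6 to 98.2 | 55.5 to 99.7 |
| 8/10 | 55.2 to 104.8 | 49.0 to 94.3 | 44.4 to 97.5 |

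For n/n successes the exact lower limit is 0.025^(1/n): 48% (n=5), 59% (7), 69% (10), 83% (20).

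**How often Wald breaks down at n = 10.** The interval has zero width or leaves 0 to 100% when X ≥ 8 or X ≤ 2. The probability is 18%, 18%, 68% and 93% at true rates of 40%, 60%, 80% and 90%. The only related rate in the documents is 8 of 20 = 40%: "secondary technique effectiveness in 8 (3.62%) patients, and the remaining 12 (5.43%) patients suffered from incomplete ablation". That describes a second session after incomplete ablation, not re-ablation for LTP. At n=5 every possible result breaks down. At n=20 the probability is 41% at a true rate of 80% and 87% at 90%.

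**Coverage by exact binomial summation, averaged over true rates 40% to 95%.** Wald: 73% (n=5), 79% (7), 84% (10), 90% (20). Wilson: 95% to 96%.

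**Full set, subject level, true rates 90% to 98%, n = 125.** Wald averages 91.6% and Wilson 95.3%. The Wald lower limit is too high in 7.6% of cases and the upper limit too low in 0.8%, against a nominal 2.5% each, so most misses favour the device. Limits move little: 117/125 gives Wald 89.3 to 97.9 and Wilson 87.9 to 96.7. For LTP at 5.9% and n=125, Wald covers 93%.

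**Run-in set, n = 12, only if Wald is carried over.** The cited rates are per tumour; for example, the 91.6% comes from a series in which "A total of 107 HCCs in 75 patients were treated via percutaneous approach". Converting with 0.75p + 0.15p² + 0.10p³:
- 91.6% becomes 89.0%, 93.6% becomes 91.5% and 97.1% becomes 96.1%. (Protocol 4.1.1 prints 97.1%, but its fraction 1276/1363 is 93.6%.)
- Wald coverage is then 75%, 65% and 38%.
- The chance of 12/12 is 25%, 35% and 62%. Wald then gives 100 to 100, against an exact lower limit of 73.5%.

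**Tumour level.** Beta-binomial simulation with 125 patients, the same tumour mix (mean 169 tumours, 1.35 per patient, matching 1363/1007) and true rates 90% to 98%. Wald covers 92.4%, 91.4%, 89.9% and 88.2% at assumed within-patient correlations of 0, 0.1, 0.3 and 0.5.

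**The case against.** The strongest reply is that little depends on these limits. There is no hypothesis and no success criterion, counts and percentages are printed beside every interval, and at n=125 a Wald interval is conventional. This stands and sets the severity.

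The expected number for secondary efficacy is an assumption. A constant-hazard extrapolation to 36 months gives 14 to 19 subjects with LTP before excluding those not re-ablated with Certus. At n=14, Wald covers 92% to 94% at true rates of 40% to 80%; at n=20 it covers 92% to 96%. Coverage falls clearly only near 90%, to 76% and 88%. The documents give no secondary-efficacy rate that high. This also stands: the poor coverage is conditional on n and the true rate. But zero width at 0% or 100%, and limits above 100% with one or two failures, occur at any n from 5 to 20.

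The main LTP estimate is Kaplan-Meier with Greenwood intervals, so the crude Wald proportion is supplementary. The plan promises no run-in interval and names no method for subgroups or sites. Those are requests to state a method and do not show that Wald is planned there.

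The documents give no within-patient correlation, and the subject-level analyses of Technical Success and Technical Efficacy already avoid clustering. That limits the clustering point to the tumour-level intervals.

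Software might cut limits at 100%, but the SAP does not say so, and truncation would not repair a zero-width interval.

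**Conclusion.** The concern holds and is minor. The SAP states a rule that gives zero-width intervals, limits above 100% and below-nominal coverage for some of its own endpoints. Secondary efficacy is most affected: average coverage is 73% to 90% for n from 5 to 20. In the full set the effect is an average of 91.6% and shifts of 1 to 2 points. Clustering costs tumour-level intervals about 1 to 4 further points. The secondary-efficacy figures rest on the assumed 5 to 20 subjects and the chosen 40% to 95% range of true rates. The run-in figures rest on the assumed tumour mix and on Wald being carried over. The tumour-level figures rest on the assumed mix and correlations. Only reported precision is affected, since no decision rule uses these limits.

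**What to change.** In SAP 8.4.1, replace Wald with Wilson (or Clopper-Pearson) for all crude proportions. State that the same method applies to secondary efficacy and to any run-in, subgroup and site intervals, including results of 0% and 100%.

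For tumour-level proportions, use a Wilson interval on an effective sample size: tumours divided by the patient-cluster design effect, with that effect not below 1, and the patient count if there are no failures. In simulation under the assumptions above, this averages 94.7% to 95.6% coverage for correlations of 0 to 0.5.

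The cost is SAP wording and SAS options (PROC FREQ BINOMIAL with WILSON or EXACT; PROC SURVEYFREQ with patient as cluster and Wilson limits), plus programming the rules for the design-effect floor and for no failures. No new data are needed. Lower limits become about 1 to 2 points less favourable in the full set, and much lower in the small sets when nearly all subjects succeed.
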